4.2. Secondary Endpoint Analysis: Effect on At-Risk Coverage

We will implement analogous analyses to assess the SEARCH effect on coverage during periods of self-reported HIV risk. We will use the same approach for effect estimation, statistical inference, and multiple testing. We will conduct analogous subgroup and sensitivity analyses.

4.3. Secondary Endpoint Analysis: Effect on HIV Incidence

A key secondary endpoint is incident HIV infection. For each participant, we will calculate person-time-at-risk (PT) as the difference between enrollment into the extension and

Last negative HIV test for persons who did not acquire HIV

Imputed HIV infection date, defined as the midpoint between last negative and first positive test, for persons who did acquire HIV.

We will then compare the HIV incidence rate, defined as the sum of incident infections divided by the sum of PT, between randomized arms with the unadjusted effect estimator. Due to the anticipated rarity of the outcome, we will not apply TMLE for additional precision gains.

Our approach to inference will be implemented analogously to the primary endpoint.

As before, the primary comparison will be on the absolute scale (i.e., the difference in the incidence rates between arms) with secondary comparisons on the relative scale. Again, standard error estimation will be based on the estimated influence curve, accounting for clustering and inference based on the Central Limit Theorem. We will test the null hypothesis of no difference in HIV incidence rates with a two-sided test at the 5% significance level. In sensitivity analyses, we will, instead, use the non-parametric bootstrap for standard error estimation and exact tests for inference. We will repeat these analyses within groups defined by sex and age group. However, we will not conduct hypothesis testing for these groups.

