This extension describes a 48-week extension of 3 ongoing randomized trials in SEARCH Phase A studying a patient-centered “Dynamic Choice Prevention” (DCP) implementation strategy for delivering existing evidence-based biomedical prevention interventions vs. standard of care (SOC). The Dynamic prevention model offers participants choices on prevention modality on an ongoing basis: oral PrEP, or oral PEP, and the option to switch between products. The trials are being conducted in 3 settings: antenatal (ANC) clinics, the outpatient department (primary care clinics), and in rural community settings in Western Uganda and Kenya. All clinic and village health team staff (i.e., Clinical Officers, nurses, coordinators, health workers) are trained and equipped for HIV prevention care in the clinical setting, appropriate to their role.

In this extension study, participants in the intervention and control arms are reconsented and remain in their initial randomized arm. Persons in the intervention arms who remain HIV negative will be offered CAB-LA as an additional biomedical prevention option, if eligible. CAB-LA will be delivered at health clinics. The primary 48-week endpoint for this extension is proportion of time covered by a biomedical prevention product. As of May 9, 2022, a total of 1213 HIV-negative persons aged 15 years and older and at risk for HIV acquisition were enrolled in the studies. (Table 1). New participants are currently being enrolled in the original SEARCH SAPPHIRE DCP trials to replace those participants who have moved or have been unable to continue in the DCP study. The total number of participants in the study eligible for CAB-LA will not exceed the 593 listed in Table 1.

Table 1. Enrollment in 3 SEARCH Sapphire Dynamic Prevention Trials as of May 9, 2022

Dynamic Prevention Study	Intervention and Control, (N) Uganda	Intervention (N) Uganda	Intervention and Control, (N) Kenya	Intervention (N) Kenya	Total Enrolled (N), Intervention and Control	Total Enrolled Intervention (N)
Antenatal/SRH Clinic	200	100	201	103	401	203
Outpatient Department Clinics	201	100	201	97	402	197
Household Study Community Village Health Team (VHT)	200	83	210	110	410	193
All Trials Together	601	283	612	310	1213	593

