7. INTERVENTION

7.1 Study Design and Schema

Study Design: This proposal is an **extension of 3 ongoing randomized trials comparing a patient-centered “Dynamic Choice” implementation strategy for delivering biomedical prevention options compared to standard of care** (Figure 1). Each trial is enrolling persons 15 years of age and older who are HIV uninfected and at risk of acquiring HIV. The Dynamic Choice Prevention intervention allows choice of PEP/PrEP, refill schedule, service delivery location (e.g. clinic, community, home), and HIV testing (self or staff). Persons can move from PEP to PrEP as they prefer.

Figure 1. Dynamic Choice Implementation Strategy.

Intervention: In the extension phase, participants will remain in their initial randomization arm. For persons in the intervention arm, CAB-LA will be integrated into the dynamic choice delivery model as an additional biomedical prevention option in a patient-centered delivery model based on the precede framework.

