4.1. Primary Analysis: Effect on Biomedical HIV Prevention Coverage

The primary endpoint of biomedical HIV prevention coverage will be compared between arms with targeted minimum loss-based estimation (TMLE) to improve efficiency over the unadjusted effect estimator.⁴⁻¹² Briefly, TMLE combines estimates of the outcome regression (i.e., the conditional expectation of the outcome, given the intervention and

covariates) and the known propensity score (i.e., the conditional probability of the intervention, given the covariates) to obtain doubly-robust inference for the estimand of interest.

The primary analysis will adjust for recruitment setting (antenatal clinic, outpatient department, or community) in the outcome regression and adaptively adjust for additional baseline covariates to optimize precision, while preserving Type-I error control. Specifically, we will use Adaptive Pre-specification to select the candidate TMLE that maximizes empirical efficiency.^{8,10,12} Using 10-fold cross-validation, we will select from the following prespecified candidates:

Outcome regression estimators: generalized linear models (GLMs) adjusting for a single covariate (beyond setting), main terms GLM, LASSO, or no further adjustment.

Propensity score estimators: GLMs adjusting for a single covariate, main terms GLM, LASSO, or no adjustment

Candidate variables: sex, age, alcohol use, mobility, or nothing

The primary analysis will estimate the marginal effect on the absolute scale (i.e., the difference in the average of the arm-specific outcomes). Secondary comparisons will be on the ratio scale. Standard error estimation will be based on the estimated influence curve, accounting for clustering from the community-based setting.^{9,10,13-15} Statistical inference will follow from the Central Limit Theorem.⁴ Specifically, we will create Wald-type 95% confidence intervals and test the null hypothesis of no difference in biomedical HIV prevention coverage with a two-sided test at the 5% significance level. We will also report point estimates and 95% confidence intervals for the arm-specific estimates.

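### HIV incidence is compared by crude pooling over three separately randomised trials; stratifying by recruitment setting is an almost free improvement, though the likely distortion is small

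*SAP*

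**What the plan says.** Protocol 7.1 describes the study as an "extension of 3 ongoing randomized trials comparing a patient-centered" strategy with standard of care. The three trials recruited in antenatal clinics, outpatient departments and the community, and participants keep their original arm.

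For the primary coverage endpoint, SAP 4.1 states: "The primary analysis will adjust for recruitment setting (antenatal clinic, outpatient department, or community) in the outcome regression". SAP 4.2 carries the same approach over to at-risk coverage.

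For HIV incidence, SAP 4.3 compares "the sum of incident infections divided by the sum of PT, between randomized arms with the unadjusted effect estimator". The reason given for not adjusting is: "Due to the anticipated rarity of the outcome, we will not apply TMLE for additional precision gains". The comparison is inferential: "We will test the null hypothesis of no difference in HIV incidence rates with a two-sided test at the 5% significance level". Clustering enters through the variance only: "standard error estimation will be based on the estimated influence curve, accounting for clustering and inference based on the Central Limit Theorem". The sensitivity analyses "use the non-parametric bootstrap for standard error estimation and exact tests for inference". They change the standard error and the test, not the estimate. The subgroup analyses are by sex and age, without testing.

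SAP Section 6 accepts that the arms may be out of balance when the extension starts, and sets out analyses to deal with this. It applies them to the two coverage endpoints only.

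**The concern.** Randomisation took place inside each trial, so the comparison that randomisation supports is the one within setting. A crude pooled rate weights each setting by its share of that arm's person-time. If those shares differ between arms and HIV risk differs between settings, the crude contrast contains a component that has nothing to do with the intervention.

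The settings do recruit different people. In Protocol Table 2 the intervention arm is 100% female in the antenatal trial, against 60.4% (outpatient) and 57.2% (community). Different HIV risk is therefore plausible, although the documents give no incidence by setting.

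The reason given for leaving out adjustment concerns precision. It does not address setting mix, and it does not rule out stratification, because Mantel-Haenszel rate methods remain usable when strata hold few events. At stake is how the point estimate and ratio of a tested endpoint are read when few infections are expected.

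**Working it through.** The SAP states no rate, event count or power for HIV incidence, so there is no figure of its own to reproduce. The check is how far the crude contrast moves when the intervention does nothing.

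**Inputs from Protocol Table 1 (9 May 2022).** The antenatal row reads "Antenatal/SRH Clinic 200 100 201 103 401 203"; the last two figures are the total and the intervention count. Control counts follow by subtraction.

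| Setting | Intervention | Control | Intervention share | Mix, intervention v control |
|---|---|---|---|---|
| Antenatal | 203 | 401 − 203 = 198 | 50.6% | 34.2% v 31.9% (+2.3 points) |
| Outpatient | 197 | 402 − 197 = 205 | 49.0% | 33.2% v 33.1% (+0.2) |
| Community | 193 | 410 − 193 = 217 | 47.1% | 32.5% v 35.0% (−2.5) |
| All | 593 | 620 | 48.9% | |

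**Assumptions.** Setting rates r_s are the same in both arms (no effect). Each continuing participant contributes 48/52 year. Continuation is 70% (SAP Section 7) unless varied. Neither setting rates nor continuation by arm and setting are in the documents, so a range is shown.

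**Formulas.** With n_s randomised and continuation c_s in an arm:
- crude rate = Σ r_s n_s c_s / Σ n_s c_s
- person-time T = (48/52) Σ n_s c_s
- SE of the difference, per 100 PY = 100 × √(R1/(100·T1) + R0/(100·T0)), where R1 and R0 are the crude rates per 100 PY. Clustering is ignored; allowing for it would normally enlarge the SE.

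**Worked case.** Rates 0.5/1.5/3 and 70% throughout:
- Intervention: (0.5×203 + 1.5×197 + 3×193)/593 = 976/593 = 1.646.
- Control: (0.5×198 + 1.5×205 + 3×217)/620 = 1057.5/620 = 1.706.
- T1 = 383.2 and T0 = 400.6 PY, so SE = 100 × √(0.01646/383.2 + 0.01706/400.6) = 0.925.
- Difference −0.060, ratio 0.965, 0.06 SE. Expected infections are about 6.3 and 6.8.

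| Rates per 100 PY (antenatal/outpatient/community) | Continuation | Crude rates, intervention v control | Difference | Ratio | Difference in SEs |
|---|---|---|---|---|---|
| 0.5/1/1.5 | 70% all | 0.992 v 1.015 | −0.024 | 0.977 | 0.03 |
| 0.5/1.5/3 | 70% all | 1.646 v 1.706 | −0.060 | 0.965 | 0.06 |
| 0.3/0.3/3 | 70% all | 1.179 v 1.245 | −0.066 | 0.947 | 0.08 |
| 0/0/3 | 70% all | 0.976 v 1.050 | −0.074 | 0.930 | 0.10 |
| 3/0/0 | 70% all | 1.027 v 0.958 | +0.069 | 1.072 | 0.10 |
| 0.5/1.5/3 | community 60% v 80%, others 70% | 1.580 v 1.767 | −0.187 | 0.894 | 0.20 |
| 0.5/1.5/3 | community 80% v 60%, others 70% | 1.706 v 1.638 | +0.069 | 1.042 | 0.07 |
| 0.3/0.3/3 | 80/70/60% v 60/70/80% | 1.051 v 1.375 | −0.324 | 0.764 | 0.41 |

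**Effect on the test.** A shift of δ standard errors gives a two-sided error rate of Φ(−1.96+δ) + Φ(−1.96−δ): about 5.1% at 0.10, 5.5% at 0.20 and 7.0% at 0.41.

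**Stratified alternative.** The Mantel-Haenszel rate difference is Σ w_s d_s / Σ w_s, where w_s = T1s·T0s/(T1s+T0s) and d_s is the within-setting rate difference. Every d_s is 0 in these scenarios, so the result is 0 (ratio 1.00) in each row. That follows from assuming equal risk by arm within each setting; it is not evidence that the estimator removes other imbalance.

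**The case against.** The best defence is size. Enrolment was nearly even in every trial, the setting mixes differ by at most 2.5 points, and the resulting shift is negligible beside sampling error. This stands. If the allocation ratio was the same in all three trials (the documents supplied do not state it), crude pooling is not biased by design, and only chance or differential continuation can shift the mix.

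The plan also has a coherent reason. SAP 4.1 presents covariate adjustment as a gain in efficiency, and with few infections little would be gained. This stands as far as it goes. However, Protocol 21.1 says the adjusted coverage comparison accounts for the stratified randomisation, and that reason applies equally to incidence.

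There are partial safeguards: blinded simulations of Type I error for all endpoints (SAP 4.1), and the bootstrap and exact tests. None of them brings setting into the estimate. Protocol 21.1 also lists incidence among descriptive analyses, but the SAP tests it at 5%.

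A reader might infer that crude pooling could create an arm difference indistinguishable from a real effect. The documents do not support that. The Table 1 splits give about 0.1 SE at most. The larger figures need assumed setting gradients together with assumed opposite continuation by arm; the SAP gives only one overall 70% figure.

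**Conclusion.** The omission is real, and its likely effect is small. Under no true effect, the Table 1 splits with equal continuation give a crude ratio of about 0.93 to 1.07 over the assumed rates, at most about 0.1 SE, with error near 5.1%. The shift reaches 0.2 SE (ratio 0.89) at rates of 0.5/1.5/3 with 60% v 80% community continuation, and 0.41 SE (ratio 0.76) in the most extreme continuation scenario tried.

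Table 1 predates re-consent, and extension enrolment by arm and setting is not given, so a larger imbalance can be neither shown nor excluded. It is not far-fetched: the trial is open-label, and the study offers CAB-LA in the intervention arm only.

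A reader might also infer that stratification would clear the comparison of any spurious difference. It would not. It removes the setting-mix component only. If the people who continue differ in HIV risk by arm within a setting, that difference remains. The point is therefore an inexpensive improvement to a tested endpoint, not an error that undermines the plan.

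**What to change.** In SAP 4.3:

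- Make the main comparison the Mantel-Haenszel rate difference stratified by recruitment setting (antenatal, outpatient, community), with the Mantel-Haenszel rate ratio as secondary and the variance clustered for the community trial.
- Keep the crude pooled contrast as a sensitivity analysis.
- Tabulate infections and person-time by arm and setting, so that a reader can see the mix.
- State that stratification does not correct for differential continuation by risk within a setting.

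The cost is a few sentences of SAP text and a few lines of code. Setting is already recorded, no new data are needed, and sparse strata are not an obstacle to the method.

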5. ADDITIONAL DESCRIPTIVE ANALYSES

We will summarize participant follow-up, overall and by arm. Follow-up in the CAB-LA extension study starts at enrollment and ends at the earliest of HIV diagnosis, death, withdrawal, or December 31, 2023. Follow-up time is censored during periods without data on use of biomedical HIV prevention.

Overall and by arm, we will report the number and proportion of participants who withdrew, died, or had other adverse events. We may also report on outcomes among women who become pregnant after initiating CAB-LA. We will summarize data on biomedical HIV prevention product use by arm. These summaries will exclude participants without any follow-up data on biomedical prevention use. We will use heatmaps to depict participant-level use of prevention products over months of follow-up in the extension. We will also provide descriptive statistics about product use over time, including the month prior to the extension study, at baseline in the extension study, and ever use during the extension study. When calculating these descriptive statistics, missing values at baseline product use will be imputed from the first follow-up month.

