7.3 Measurement

Outcomes: The primary outcome for the extension is the proportion of time covered by a biomedical prevention option during the 48 week follow-up period of the CAB-LA Extension; follow-up time will be censored at HIV diagnosis, death, or withdrawal. Biomedical covered time is defined as the proportion of follow-up time that each participant is covered by either PrEP (TDF/3TC or CAB-LA) or PEP. For TDF/3TC, covered time is defined using self-reported use; in a subset of participants who report PrEP use we will measure tenofovir drug levels using small hair samples to allow for calibration of self-reported measures. For CAB-LA, coverage begins 3 days after initial injection continues 2 months + 7 days after last injection. For PEP, covered time is defined using self-reported use; in a subset of participants who report PEP use we will measure drug levels using hair samples to allow for calibration of self-reported measures. A secondary outcome for the extension is “at-risk covered time”, defined as the proportion of time that a participant reports being at risk of HIV infection during which they are covered by a biomedical prevention option. Incident HIV infections, defined by a prespecified testing algorithm, will be an additional secondary outcome.

Secondary outcomes of reach, effectiveness, adoption, implementation and maintenance will be evaluated using a mixed methods approach that includes surveys of participants, and health center providers and staff. Tertiary outcomes of knowledge, awareness and acceptability/satisfaction at the staff and provider level will be measured by surveys at the baseline, midpoint and end of the study. Measurement details are delineated in Table 4 .

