7.3.2 Costing Evaluations

Costing of CAB-LA implementation will be conducted in each region and location type (Antenatal Clinic, Outpatient Department, Community) at Baseline/Screening and at two injection visits during follow-up. Costing exercises will employ an activity-based approach and include site visits and employ rigorous costing methods using standardized micro-costing tools.

We will also conduct time-and-motion activities using self-administered tools with on-site staff to estimate the amount of time spent implementing CAB-LA. We will interview study staff to identify resources used to implement the intervention and estimate time spent providing oversight and management of implementation activities.

Implementation Research Design: The secondary objective of the extension is an implementation evaluation of the intervention focused on the initial implementation of patient-centered CAB-LA using the RE-AIM framework. The domains of interest and key outcomes are summarized in the table below. Throughout, study weeks are used to refer to weeks in CAB-LA extension (eg, “week 0” is date of re-consent for the CAB-LA extension, “week 48” is 48 weeks after re-consent for the CAB-LA extension).

Table 4. RE-AIM Evaluation Framework.

Domain /Outcome	Definition	Measurement	Timing
Reach (Participant level)	Proportion of eligible participants who initiate CAB-LA weeks 0-48. Characteristics (including prior PrEP and PEP use) and attitudes (knowledge, acceptability and feasibility) of participants using CAB-LA	Demographics, CAB-LA dispensing logs Knowledge, Acceptability and Feasibility (Survey and IDI). Evaluation includes focus on equitable access by gender, education and SES.	CAB LA dispensing throughout follow-up Surveys and IDI: Week 0, 24 and week 48
Effectiveness (Participant level)	Impact of adding CAB-LA to Dynamic choice prevention on biomedical covered time (comparison of follow-up during the CAB-LA extension vs. follow-up time in Phase A trials prior to CAB-LA extension).	CAB-LA dispensing logs, PrEP and PEP use as defined for primary endpoint in extension.	Throughout follow-up

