21.1 Overview

This section provides an overview of the statistical consideration.

The primary study endpoint in this extension will be biomedical covered time defined as the proportion of follow-up time that the participant is protected from HIV infection by any PEP or PrEP (inclusive of CAB-LA). Follow-up will be over the 48 weeks following re-consent for the CAB-LA extension. At risk covered time will be a secondary outcome, defined as the proportion of at-risk follow-up time that the participant is protected from HIV infection by any PEP or PrEP (inclusive of CAB-LA). We will also conduct sensitivity analyses, varying the definitions of coverage and risk. For example, we will also examine covered time from CAB-LA only (i.e., exclusive of oral PrEP or PEP), and we will conduct a sensitivity analysis in which we treat time after loss to follow-up among persons not known to have moved out of the study region and time after study withdrawal as presumed to be non-covered.

For our primary objective in this extension, we will compare covered time during the 48 week CAB-LA extension between the intervention and control arms. For improved efficiency, Targeted Maximum Likelihood Estimation (TMLE) will be used to adjust for differences in baseline participant characteristics between the two trial arms, accounting for the stratified randomization design. In secondary analyses, we will further use TMLE to i) adjust for measured differences between arms at time of start of the CAB-LA extension period; and, ii) adjust for baseline and time-varying factors that are predictive of the outcome and that differ between persons that do vs. do not have their follow-up time censored. The primary analysis will pool over the trials, accounting for clustering inherent in the community trial; secondary analyses will stratify by trial site. We will test the null hypothesis that covered time is the same between arms with a two-sided test at the 5% significance level.

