1. OVERVIEW OF THE SEARCH CAB-LA EXTENSION STUDY

This study is testing the hypothesis that a “Dynamic Choice HIV Prevention” intervention that offers participants CAB-LA, oral Pre-Exposure Prophylaxis (PrEP), or post-exposure prophylaxis (PEP) and the ability to switch between products over time using a patient-centered delivery approach will achieve higher prevention coverage for males and females ≥ 15 years of age and at risk for HIV infection acquisition, as compared to the country standard-of-care (SoC). The current SoC for biomedical HIV prevention includes oral PrEP and PEP. This study is being conducted in rural western Uganda and rural western Kenya. The follow-up is over 48 weeks. Additional details of the study design, arms, and procedures can be found in the Study Protocol.

[figure not shown]
The primary objective is to evaluate the effect of the Dynamic Choice HIV Prevention intervention versus the SoC on biomedical HIV prevention coverage, defined as the proportion of follow-up time covered by either PrEP (oral PrEP or CAB-LA) or PEP. Secondary, pre-specified endpoints compared between arms and included in this SAP are coverage during periods of self-reported risk of HIV acquisition (“at-risk coverage”) and HIV incidence. We additionally describe product use over time between arms. Analysis plans for other endpoints (e.g., implementation metrics and the change in endpoints before and after adding CAB-LA to the intervention) are available elsewhere. Power calculations and history of changes are given in the Appendix.

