2. POPULATION AND CHARACTERISTICS

The study population is persons who were enrolled in the 3 randomized Dynamic Choice HIV Prevention trials that recruited from antenatal clinics, outpatient departments, and the community.¹⁻³ These trials were designed to evaluate the impact of the Dynamic Choice HIV Prevention intervention (offering choice between oral PrEP and

PEP as biomedical HIV prevention options) versus the SoC on biomedical HIV prevention coverage over 48 weeks (Figure 1).

Figure 1: Schematic of the CAB-LA extension study with abbreviations of DCP for Dynamic Choice HIV Prevention intervention and SOC for standard-of-care.

The Dynamic Choice HIV Prevention trials enrolled participants aged ≥ 15 years with current or anticipated risk to acquire HIV. Inclusion criteria for the CAB-LA extension study are 1) Prior enrollment in a SEARCH Dynamic Choice HIV Prevention trial, 2) HIV-negative by country-standard rapid HIV testing algorithm, and 3) Residence in the study region. In the extension, participants maintained their original randomization arm and are not blinded to the treatment arm. The primary statistician ([name]) will remain blinded to the treatment arm until the official unblinding of the study when the primary and secondary effect analyses, described in this SAP, are conducted. Additional details, including randomization procedures and eligibility for CAB-LA access among intervention arm participants, are in the Study Protocol.

To characterize participant flow from original randomization through measurement of the primary endpoint of the extension, we will provide a CONSORT diagram. To describe the study population, we will summarize participant characteristics at start of the extension, overall and by arm. These characteristics will include recruitment setting, country, sex, age, marital status, occupation, pregnancy (women only), circumcision (men only), and alcohol use (having 1+ alcoholic drink per week).

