7. POWER CALCULATIONS

We assume 70% of participants in the 3 Dynamic Choice HIV Prevention trials enroll in the extension. Of those, we assume 90% have measures of biomedical HIV prevention coverage (the primary endpoint). Then using standard formulas for continuous outcomes with clustering,^{20,21} we anticipate at least 80% power to detect at least a 7.5% absolute increase in prevention coverage with 485 participants/arm, an outcome standard deviation of 0.35, and a design effect of 1.3. As shown in Figure 2, these calculations are fairly robust to alternative assumptions, including lower outcome measurement

and higher design effects. We further expect these calculations to be conservative given the precision gains due to covariate adjustment with TMLE in the primary analysis.

Figure 2: Minimal effect size (difference) detected with 80% power with a two-sample t-test (via `power.t.test` in R) after deflating the sample size by the design effect

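### SAP section 5 stops follow-up on a calendar date with no 48-week limit, so time counted in the primary endpoint can be shorter or longer than the stated 48 weeks and can differ by arm

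*SAP*

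**What the plan says.** - **Length of follow-up.** SAP section 1: "The follow-up is over 48 weeks". Protocol 7.3 gives the primary outcome as the "proportion of time covered by a biomedical prevention option during the 48 week follow-up period of the CAB-LA Extension". Protocol 21.1: "Follow-up will be over the 48 weeks following re-consent for the CAB-LA extension". Protocol 7.3.2 sets time zero: week 0 "is date of re-consent for the CAB-LA extension".
- **End of follow-up.** Protocol 7.3 censors at HIV diagnosis, death or withdrawal and gives no calendar date. SAP section 5 says that follow-up "ends at the earliest of HIV diagnosis, death, withdrawal, or December 31, 2023". It also censors periods that have no data on product use.
- **Endpoint.** SAP 3.1 takes the share of each participant's follow-up time that is covered. It does not define follow-up time again, so the section 5 sentence sets the denominator even though it stands under descriptive analyses.
- **Data sources.** Under SAP 3.1, oral PrEP and PEP use comes from surveys at weeks 24 and 48, each looking back six months. CAB-LA coverage comes from injection logs.
- **Visits.** Protocol Table 5, footnote 4, accepts a Week 48 visit from week 40 to week 56. Under protocol 9.1, control participants consent to visits at weeks 24 and 48 only. Under protocol 8.1, intervention participants may continue to Week 96, and those on CAB-LA at Week 48 may stay on it, if CAB-LA is not yet available in country.

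**The concern.** The endpoint is stated over a fixed 48 weeks per person, but the operative rule is one calendar date for everyone. For a participant with no earlier event, the two agree only if enrollment fell on exactly January 29, 2023. Later entrants are cut short and earlier entrants are not capped.

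Two things are at stake. First, the time point: the result would be reported as 48-week coverage while averaging proportions taken over different lengths of time. The protocol notes in 4.1 that PrEP use fell over time in an earlier study, and in 8.1 it lets CAB-LA start at any point in the 48 weeks, so early and late coverage need not be alike. Second, balance between arms: where no survey covers a period, oral use is unknown and the time drops out, but CAB-LA injections are still logged. The study supplies CAB-LA in the intervention arm only, so the time that survives outside the surveyed periods can be mostly covered time in that arm. The same rule feeds at-risk coverage.

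**Working it through.** **1. The plan's own power figure (SAP section 7).** Inputs: 485 per arm, SD 0.35, design effect 1.3, difference 0.075, two-sided 5%.
- Effective n = 485 / 1.3 = 373.1 per arm.
- Standard error = 0.35 × √(2 / 373.1) = 0.0256.
- Power = Φ(0.075 / 0.0256 − 1.96) = 83.3%, which agrees with the stated 80% or more. If the 90% measurement assumption is applied on top of the 485, power is 79.3%.

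This calculation does not use the length of follow-up. It serves below as a yardstick.

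**2. Entry dates implied by the stop.** Latest entry = December 31, 2023 minus the required weeks.

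| Follow-up needed | Latest entry |
|---|---|
| 24 weeks | July 16, 2023 |
| 40 weeks (earliest Week 48 visit) | March 26, 2023 |
| 48 weeks | January 29, 2023 |
| 56 weeks (latest Week 48 visit) | December 4, 2022 |

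**3. Potential follow-up by entry date.** Days to December 31, 2023, divided by 7.

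| Entry | Weeks available |
|---|---|
| November 1, 2022 | 425 / 7 = 60.7 |
| January 1, 2023 | 364 / 7 = 52.0 |
| January 30, 2023 | 335 / 7 = 47.9 |
| February 28, 2023 | 306 / 7 = 43.7 |
| March 31, 2023 | 275 / 7 = 39.3 |
| June 30, 2023 | 184 / 7 = 26.3 |

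Neither document gives extension entry dates or closes entry by a date, so these are possibilities and not counts.

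**4. Truncation alone.** Assume the arm difference falls linearly from d to 0.5d over 48 weeks. Its mean up to week t is d × (1 − 0.25 × t / 48).
- At 48 weeks: 0.750d.
- At 43 weeks: 0.776d, or 3.5% too high. If every participant were cut there, a 7.5-point effect would be overstated by 0.035 × 7.5 = 0.26 points.
- At 40 weeks: 0.792d, or 5.6% too high, which is 0.42 points if everyone were cut.

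If the difference instead grows by half, the mean is d × (1 + 0.25 × t / 48). At 40 weeks that is 1.208d against 1.250d, or 3.3% too low. These shifts scale with the share of participants cut. They compare with a standard error of 2.6 points, and the direction is not known.

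**5. Time outside the surveyed periods.** Illustrations for one intervention participant, assuming 70% coverage in the surveyed time and continuous CAB-LA coverage afterwards.
- Early entrant, November 1, 2022. Capped at 48 weeks: 70%. As written: (0.70 × 48 + 12.7) / 60.7 = 46.3 / 60.7 = 76%.
- Late entrant, March 31, 2023, with no Week 48 survey by the stop. Surveyed weeks only: 70%. As written: (0.70 × 24 + 15.3) / 39.3 = 32.1 / 39.3 = 82%.

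A control participant in the same position has no study injection log, so the extra time is censored and the figure stays at the surveyed value. This is the part of the problem that does not cancel between arms.

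For the early entrant, a 48-week cap removes the extra time. For the late entrant, the cap does not act, and the entry-date sensitivity analysis is what tests the effect.

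**The case against.** The strongest reply is that no late entrant is shown. Entry dates are absent, and everyone may have enrolled by January 29, 2023. That stands, and it makes the late-entry half conditional. It does not touch the missing cap: if everyone enrolled early, more people can exceed 48 weeks.

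Second, the endpoint is a proportion of each person's own follow-up, and unequal follow-up is already accepted through censoring. This also stands. A reader might infer that late entrants are scored as if they had completed 48 weeks, or as uncovered after the stop. The documents do not support that, because their denominator is simply shorter.

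Third, a reader might try to size the late group. Replacement enrollment was open in May 2022 ("New participants are currently being enrolled in the original SEARCH SAPPHIRE DCP trials to replace those participants who have moved"), the parent endpoint runs 48 weeks ("PEP as biomedical HIV prevention options) versus the SoC on biomedical HIV prevention coverage over 48 weeks"), and SAP section 7 says "We assume 70% of participants in the 3 Dynamic Choice HIV Prevention trials enroll in the extension". Working back from 2 × 485 = 970 gives a parent total of 970 / 0.70 = 1386 or 970 / (0.70 × 0.90) = 1540, against 1213 on May 9, 2022, and so 12.5% to 21% who joined the parent trials later. This does not hold as an estimate of late extension entry. The 70%, the 90% and the 485 are planning figures, and 970 is also 80% of 1213. Nothing requires the parent Week 48 to come first: eligibility in protocol 5.2 and SAP section 2 asks for enrollment in a parent trial, and protocol sections 3 and 8.1 tie re-consent to study approval and CAB-LA availability.

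Fourth, some protection is planned. SAP section 5 summarises follow-up by arm, and SAP 4.1 has a sensitivity analysis limited to surveyed periods. That analysis bears on step 5 above, but it leaves the primary result unchanged. Its presence also implies that the primary analysis keeps time outside the surveys.

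Fifth, an analyst may intend a 48-week cap, or may use surveys taken after the stop to fill in earlier months. Either would shrink the problem. The SAP states neither.

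**Conclusion.** The point holds as a conflict between a stated rule and the stated endpoint. The SAP's follow-up rule gives 48 weeks only for entry on January 29, 2023; later entry gives less and earlier entry can give more. Nominal Week 48 visits remain possible for entry up to March 26, 2023, so the loss for people who entered between those two dates is limited.

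The number affected cannot be computed, and there may be no late entrants. Truncation alone is probably small: under the assumed patterns it is under half a point even if everyone were cut at 40 weeks, against a standard error of 2.6 points. The arm-differential retention of CAB-LA time is the more serious route. It raised one intervention participant's figure by 6 to 12 points in the illustrations (70% to 76% and 70% to 82%), but its effect on the arm means depends on how many participants have such time, which is not given. That route assumes that logged CAB-LA time is kept where no survey exists, which is the natural reading of SAP 3.1 and section 5 together. Correction before analysis is worthwhile because it costs so little.

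**What to change.** In SAP section 5, end follow-up at the earliest of 48 weeks after extension enrollment, HIV diagnosis, death, withdrawal and, if the date must stay, December 31, 2023. In addition:

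1. Report by arm the number and share whose potential follow-up to the stop is under 48 weeks.
2. If there are any, describe the endpoint as coverage over up to 48 weeks.
3. Add a sensitivity analysis of the primary and at-risk endpoints restricted by entry date to people with full potential follow-up: enrolled by January 29, 2023, or by March 26, 2023 if the 40-week window is used. Selection is on entry date and not on outcome.
4. Say whether a survey taken after the stop may supply data for months before it.

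The cost is one sentence and one extra analysis run, with no new visits and no delay to database lock. The restricted analysis loses some precision. On the SAP's inputs, excluding 5, 10, 20 or 30% of the 485 per arm lowers power for 7.5 points from 83.3% to 81.4, 79.3, 74.5 or 68.7%. That is acceptable for a sensitivity analysis, which should be read for agreement with the primary estimate and not for significance.
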